1 STUDY SYNOPSIS

<copy this information from last approved protocol>

Complete Protocol Title	Quattro® X Suture Anchor with BroadBand™ Tape Post Market Clinical Follow-up Study (incl. Instruments)
Protocol Number	CME2021-24SM
Short Protocol Title	Quattro® X with BroadBand
Sponsor	Zimmer Biomet, Warsaw, Indiana, United States
Manufacturer	Cayenne Medical Inc.
Study Device(s)	Quattro X Suture Anchors with BroadBand Tape - 5.5mm Quattro X Suture Anchor Double-Loaded with BroadBand Tape (Non-Sliding)
	- 6.5mm Quattro X Suture Anchor Double-Loaded with BroadBand Tape (Non-Sliding)
	- 5.5mm Quattro X Suture Anchor Double-Loaded with BroadBand Tape (Sliding)
	- 6.5mm Quattro X Suture Anchor Double-Loaded with BroadBand Tape (Sliding)
	Quattro X Suture Anchor Reusable Instruments (Non-Sterile)
	- Awl, 5.5/6.5mm Quattro X Suture Anchor
	- Tap, 5.5mm Quattro X Suture Anchor
	- Tap, 6.5mm Quattro X Suture Anchor
	The objective of the study is to collect data confirming safety, performance and clinical benefits of the Quattro® X Suture Anchor with BroadBand™ Tape and Instruments when used in rotator cuff repair.
Study Objectives/Endpoints	The primary endpoint of this study is the assessment of performance by analyzing soft tissue to bone healing in the shoulder (rotator cuff). Healing will be assessed by the investigator using PROMs and clinical outcomes of the patient.
	The clinical benefit will be assessed by functional outcomes measured using standard and well-established scoring systems (e.g. Constant & Murley and EQ-5D-5L) at 1 year post-operative.
	The safety will be assessed by monitoring the incidence and frequency of device- and/or procedure-related adverse events.

Indications/Target Population	Subjects treated with the Quattro® X Suture Anchor with BroadBand™ Tape for rotator cuff repair, according to the IFU and who meet all of the inclusion and none of exclusion criteria.
Inclusion/Exclusion Criteria	The indications/contra-indications are in line with the Instruction for Use (IFU). Inclusion Criteria: Quattro® X Suture Anchors are intended for use for the reattachment of soft tissue to bone for Rotator Cuff Repairs. 1. Subject treated with the Quattro® X Suture Anchor with BroadBand™ Tape for rotator cuff repair; 2. Older than 18 years and skeletally mature; 3. Willing and able to comply with the study procedures; 4. Subject is capable of understanding the doctor's explanations, following his instructions and is able to participate in the follow-up program; 5. Subject is able to read and understand the ICF and has voluntarily provided written informed consent. Exclusion Criteria: 1. Presence of infection; 2. Insufficient or immature bone; 3. Insufficient blood supply or previous infections which may hinder the healing process; 4. Foreign body sensitivity; 5. Subject is vulnerable (prisoner, mentally incompetent or unable to understand what participation to the study entails, a known alcohol or drug abuser, anticipated to be non-compliant); 6. The subject is unwilling or unable to give consent or to comply with the follow-up program; 7. Subject meets any contraindications of the appropriate Instruction for Use.
Study Design	Retrospective and prospective, consecutive, multicenter, non-randomized, non-controlled study
Clinical Phase	Post-market
Sample Size	Maximum of 109 study subjects implanted with the study device.
Length of Study	1 year

Materials and Methods	Retrospective inclusion of 109 subjects who are eligible for rotator cuff repair with the Quattro® X Suture Anchors with BroadBand™ Tape. Prospective follow-up visit at 1 year postoperative.
Data Collection	Paper/Electronic
Statistical Reporting	Data collected will be summarized and reported to each participating investigator. Statistical analysis will be conducted by Zimmer Biomet or its designee. Survivorship will be evaluated using Kaplan-Meier.
Scores/Performance Assessments	
Standards	 The PMCF is compliant with the below: ISO 14155: 2020 - Clinical investigation of medical devices for human subjects - Good clinical practice. The Declaration of Helsinki (DoH) - Ethical principles for medical research involving human subjects. European Regulation (EU) 2017/745
Study Funding	Funding for this clinical study is made available by Zimmer Biomet to support clinical data collection, other expenses associated with the conduct and execution of this study protocol as outlined in the fully executed Clinical Trial Agreement.

2 STATISTICAL ANALYSIS PLAN

2.1 Sample Size

The overall success rate will be calculated based on the percentage of subjects who have successful healing. The following hypothesis will be tested by the exact binomial test

H0: $E1 - E0 \le - \delta E$

Ha: E1 – E0 > - δ E

Where:

E0 = 85%, the expected success rate of similar devices

E1 = the success rate in the Quattro® X Suture Anchor with BroadBand™ Tape treatment group

 $\delta E = 0.10$, non-inferiority margin for healing

In addition, one-sided 95% exact confidence Interval (CI), lower limit of the success rate, will be calculated.

Based on the hypothesis test above, 103 subjects will provide approximately 80% power for the one-sided exact binomial test at 0.05 significant level. The sample size was calculated using SAS for Windows version 9.4. To account for an expected 5% loss-to-follow up, 109 patients will be enrolled.

2.2 General Statistical Methods

Continuous data, such as age, will be summarized by using means, medians, standard deviation, minimum, maximum, and 95% CI over the time periods of interest. Categorical data, such as gender or surgical approach, will be summarized by counts and percentages. Implant survival will be summarized using a Kaplan-Meier method and presented with rates (as percentages) and confidence intervals (CI). Statistical analyses will be performed using SAS 9.4. The binomial distribution tests will have 80% probability of computing a one-sided 95% lower confidence bound on survivorship of each device with a non-inferiority margin of 0.09. Patient confidentiality will be protected at all times, and patient identifiers will not be included in data summaries.

Handling of Missing and Incomplete Data: Data will be considered "censored" for the primary endpoint if the survivorship outcome cannot be determined or is unavailable for a subject. Every effort will be made to collect the data necessary to evaluate the primary endpoint. Patients who have been lost to follow-up will not be included in the primary study analysis at the end of 1 year. However, the data already collected will be used in interim analysis and survivorship calculations.

Sensitivity analyses will be performed to assess the impact of missing data on the primary study analysis. These analyses may include a best-case and worst-case imputation as well as a tipping point analysis.

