2.3 Data Analysis

The Per Protocol population will be defined as those subjects that undergo a successful implantation of the Quattro® X Suture Anchor with BroadBand™ Tape. Analyses on the primary and secondary endpoints will use this population as well as any exploratory analyses.

The primary endpoint will be determined at the only clinical assessment, about one year from the index surgery. The absence of a revision surgery or re-tear not previously noted on the case report form will denote a success (within 425 days from index surgery). All other cases will be a failure and have a documented revision surgery or re-tear.

Secondary analyses will include a summary of any clinical scores captured at baseline and the one year assessment; change from baseline analyses may be developed. In addition, a summary of medications and patient satisfaction may also be assessed.

Any potential exploratory analysis that assess outcomes be categories (gender, age, etc.) will use appropriate statistical test for the type of variable (i.e. t-tests, ANOVA, Fisher's Exact, etc). All testing will use a Type I error of 0.05 and no p-values will be adjusted for multiplicity.

Adverse events will also be captured at the one year assessment. Only AEs that occur on or after the index surgery and before any potential revisions or re-tears will be summarized. Adverse events will be presented as the number of cases for each AE and the number of times the give AE occurred. Finally, a complete listing of all AEs will be presented.

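### Section 2.2 claims 80% probability for a 0.09 margin on survivorship of each device, gives no reference rate, and does not reconcile it with the 0.10 margin and 80% power in section 2.1

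*Combined protocol and SAP*

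**What the plan says.** Section 2.1 sets out a complete non-inferiority test of the healing success rate. The reference rate E0 is 85% and the margin for healing is 0.10. The method is a one-sided exact binomial test with the matching one-sided 95% lower limit. It states that "103 subjects will provide approximately 80% power for the one-sided exact binomial test at 0.05 significant level", and 109 are enrolled to allow for 5% loss. The synopsis caps enrolment: "Maximum of 109 study subjects implanted with the study device".

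Section 2.2 adds a second probability statement, that the binomial tests "will have 80% probability of computing a one-sided 95% lower confidence bound on survivorship of each device with a non-inferiority margin of 0.09".

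Other text bears on what survivorship means here, and it points both ways:

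- The missing-data paragraph of 2.2 treats data as censored "for the primary endpoint if the survivorship outcome cannot be determined or is unavailable for a subject". This describes the primary endpoint as a survivorship outcome.
- Section 2.3 defines the primary endpoint in similar terms: "The absence of a revision surgery or re-tear not previously noted on the case report form will denote a success".
- The synopsis assigns survivorship to a different method: "Survivorship will be evaluated using Kaplan-Meier".
- Section 2.2 leaves patients lost to follow-up out of the primary analysis but says "the data already collected will be used in interim analysis and survivorship calculations".

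**The concern.** A power statement for a non-inferiority test needs a reference rate, a margin, a sample size and a value that the confidence bound must exceed. Section 2.1 supplies all four for margin 0.10. Section 2.2 supplies only the margin and the 80%. Read literally, it is not even a power statement, since a lower bound can always be computed. Presumably it means the probability that the bound exceeds the reference rate minus 0.09.

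Two readings are open:

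1. **0.09 applies to the primary test.** The only binomial test in the plan is the one in 2.1, and the plan describes the primary endpoint in survivorship terms.
2. **0.09 applies to a separate survivorship analysis.** The Kaplan-Meier text and the different handling of lost patients support this.

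Under reading 1 the plan has two margins for one test, and the choice between them could be made after the data are seen. Under reading 2 it makes a power claim that no reader can verify. Under either, the words about each device have no sample size behind them: 2.1 sizes a single pooled group, while the synopsis lists four anchor configurations.

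**Working it through.** **Inputs.** From 2.1: reference 0.85, margin 0.10, one-sided alpha 0.05, n = 103 evaluable, 5% loss, 109 enrolled. From 2.2: margin 0.09, one-sided 95% lower bound, claimed probability 80%. The plan gives no reference rate for 0.09.

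**Method.** With null rate p0 = reference − margin, find the smallest count c for which P(X ≥ c | n, p0) ≤ 0.05. Power is P(X ≥ c | n, p1), with p1 equal to the reference. Passing this test is equivalent to an exact (Clopper-Pearson) one-sided 95% lower limit above p0.

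**Step 1: reproduce 2.1.** p0 = 0.85 − 0.10 = 0.75, p1 = 0.85.

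| n | c | Exact alpha | Power |
|---|---|---|---|
| 103 | 85 | 0.0456 | 80.3% |
| 109 | 90 | 0.0394 | 80.4% |

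n = 103 is the first size to reach 80%, and 103/0.95 = 108.4, rounded up to 109. Section 2.1 is internally correct.

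**Step 2: reading 1, margin 0.09 on the primary test.** p0 = 0.85 − 0.09 = 0.76, p1 = 0.85.

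| n | c | Exact alpha | Power |
|---|---|---|---|
| 103 | 86 | 0.0438 | 72.2% |
| 109 | 91 | 0.0389 | 72.5% |
| 126 | 104 | 0.0496 | 81.7% |

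The first n to reach 80% is 126 evaluable. 126/0.95 = 132.6, so 133 enrolled, above the maximum of 109. Exact power is saw-toothed: it falls back to 77.3% at n = 130 and 79.9% at n = 140, and stays at or above 80% only from n = 141 (141/0.95 = 148.4, so 149 enrolled).

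**Step 3: where the two margins disagree at n = 103.** The exact lower limits are:

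- 85/103: 75.2%, which is above 75% but below 76%.
- 86/103: 76.3%, which is above both.

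The disputed result is therefore exactly 85 successes. If the true rate is 85%, P(X = 85 | 103, 0.85) = 0.081.

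**Step 4: reading 2, a separate survivorship claim.** The reference rates below are assumptions, because the plan states none. All subjects are pooled and the margin is 0.09.

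| Assumed reference | Power, n = 103 | Power, n = 109 |
|---|---|---|
| 85% | 72.2% | 72.5% |
| 90% | 77.2% | 80.1% |
| 92% | 79.9% | 83.8% |
| 95% | 92.7% | 95.3% |

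n = 109 is an upper bound here, because lost patients contribute only partial follow-up. A figure of 80% fits a pooled reference of about 90% to 92%.

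**Step 5: each device.** No number per configuration is given. As an illustration only, assume an equal split over the four configurations, 109/4 or about 27 each. With margin 0.09, power is then about 21% at an 85% reference and 35% at 92%.

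**The case against.** The strongest reply is that no calculation in the plan is shown to be wrong. Section 2.1 labels its margin as being for healing, and 2.2 attaches 0.09 to survivorship shortly after assigning implant survival to Kaplan-Meier. Different endpoints may carry different margins. The 72% figure arises only if the healing reference is joined to the survivorship margin, which no sentence does explicitly. As a separate claim, 80% could be right: it is reached at n = 109 with a 90% reference. The primary test can be run from 2.1 as written. Even under reading 1 the margins differ by at most one count, and at 97 or 102 evaluable they give the same cut-off (81 and 85).

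Much of this stands. Section 2.1 is sound, reading 2 is tenable, and under it the 80% is undocumented rather than shown to be false. The size of the disagreement does depend on the evaluable number. The absence of a reference rate can be asserted only for the text supplied, whose synopsis is an extract from the protocol. It is also fair that 126 is a first crossing and not a stable minimum.

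None of this removes the defect. The plan itself calls the primary outcome a survivorship outcome, so reading 1 cannot be excluded from the text. Under reading 2 the claim still lacks every input needed to check it. Neither reading supports a claim for each device.

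**Conclusion.** The concern holds. Section 2.2 states a power and a margin that the documented design does not support, and it leaves them unreconciled with section 2.1.

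- If 0.09 governs the primary test at the stated 85% reference, power is about 72% at 103 to 109 evaluable, against the 80% claimed. At 103 evaluable, one result (85 successes, probability about 8% if the true rate is 85%) changes the conclusion.
- If 0.09 belongs to a separate pooled survivorship analysis, the 80% cannot be verified and depends on an unstated reference rate.
- Under both readings, no sample size supports a claim for each device.

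These figures assume the exact one-sided test of 2.1, a true rate equal to the reference rate, and pooled subjects. The finding does not say that 103 evaluable or 109 enrolled is wrong for the test in 2.1.

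**What to change.** Carry one margin per test, each with its reference rate, and settle this before the data are analysed.

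- **Recommended:** keep 0.10 as the only primary margin. In 2.1, write the decision rule as an exact one-sided 95% lower limit above 75% (at least 85 successes if 103 are evaluable). Delete the sentence in 2.2 on 0.09 and each device. Cost: SAP wording only, no extra patients.
- **If 0.09 was meant for a separate survivorship analysis:** state its endpoint, reference rate, hypothesis, analysis number and actual power. Cost: SAP wording only.
- **If 0.09 was meant for the primary endpoint:** change 2.1 and restate power as about 72% at 103 evaluable. Otherwise raise enrolment from 109 to at least 133 (126 evaluable, the first size to reach 80%), or to 149 (141 evaluable) for power that does not fall below 80% at larger evaluable numbers. Raising enrolment also means changing the synopsis maximum.

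In every case, report results by anchor configuration as descriptive, with no power claim.

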2.3 Data Analysis

The Per Protocol population will be defined as those subjects that undergo a successful implantation of the Quattro® X Suture Anchor with BroadBand™ Tape. Analyses on the primary and secondary endpoints will use this population as well as any exploratory analyses.

The primary endpoint will be determined at the only clinical assessment, about one year from the index surgery. The absence of a revision surgery or re-tear not previously noted on the case report form will denote a success (within 425 days from index surgery). All other cases will be a failure and have a documented revision surgery or re-tear.

Secondary analyses will include a summary of any clinical scores captured at baseline and the one year assessment; change from baseline analyses may be developed. In addition, a summary of medications and patient satisfaction may also be assessed.

Any potential exploratory analysis that assess outcomes be categories (gender, age, etc.) will use appropriate statistical test for the type of variable (i.e. t-tests, ANOVA, Fisher's Exact, etc). All testing will use a Type I error of 0.05 and no p-values will be adjusted for multiplicity.

Adverse events will also be captured at the one year assessment. Only AEs that occur on or after the index surgery and before any potential revisions or re-tears will be summarized. Adverse events will be presented as the number of cases for each AE and the number of times the give AE occurred. Finally, a complete listing of all AEs will be presented.

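### The primary endpoint is named and tested as healing but scored only as absence of revision or re-tear, so a pass does not establish a healing rate above 75%

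*Combined protocol and SAP*

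**What the plan says.** **Synopsis (section 1, Study Objectives/Endpoints).** The primary endpoint is performance, shown by healing of soft tissue to bone in the rotator cuff. On how this is judged: "Healing will be assessed by the investigator using PROMs and clinical outcomes of the patient". No threshold is given.

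**Section 2.1.** The tested quantity is healing: "The overall success rate will be calculated based on the percentage of subjects who have successful healing". The reference is "E0 = 85%, the expected success rate of similar devices", and the 0.10 is called the "non-inferiority margin for healing". The null bound is therefore 75%.

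**Section 2.2.** The vocabulary changes. Data are censored for the primary endpoint "if the survivorship outcome cannot be determined or is unavailable for a subject". The same section speaks of "computing a one-sided 95% lower confidence bound on survivorship of each device with a non-inferiority margin of 0.09", with no reference rate. It also leaves subjects lost to follow-up out of the primary analysis.

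**Section 2.3.** The only scoring rule is here: "The absence of a revision surgery or re-tear not previously noted on the case report form will denote a success", with a limit of 425 days from surgery. Every other case is a failure with a documented revision or re-tear. Clinical scores are placed among the secondary analyses.

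**The concern.** The outcome named and tested is not the outcome scored. A subject whom the investigator judges not healed on patient-reported and clinical outcomes, but who has no recorded revision or re-tear, counts as a success under section 2.3. A re-tear does bear on healing, so the section 2.3 rate is relevant indirect evidence, but the plan nowhere makes it the definition of healing. Following section 2.3 and then reporting the section 2.1 hypothesis would state a healing result from an outcome not defined as healing.

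Three further points follow from the unsettled definition:

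1. It is unclear which outcome the 85% and the 0.10 describe, and whether the 0.09 in section 2.2 concerns the same test.
2. Read literally, the loss-to-follow-up rule in section 2.2 could remove a subject with an early documented revision or re-tear who misses the one-year visit, although section 2.3 calls that subject a failure.
3. It is unclear whether 425 days is the period over which events count or the latest permitted visit date.

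**Working it through.** **Inputs.** From section 2.1: reference E0 = 0.85, margin 0.10, one-sided exact binomial test at 0.05, 103 evaluable subjects, 5% loss, 109 enrolled. From section 2.2: margin 0.09. From the synopsis: maximum 109 subjects. From section 2.3: 425 days.

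**Step 1: reproduce the plan's figure.** The null bound is 0.85 − 0.10 = 0.75. The critical value is the smallest r with P(X ≥ r | 103, 0.75) ≤ 0.05.
- r = 85 (85/103 = 82.5%), exact alpha 0.0456.
- Power = P(X ≥ 85 | 103, 0.85) = 0.803. The first sample size to reach 0.80 is 103, as planned.
- Loss: 103/0.95 = 108.4, rounded up to 109, as planned.

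The arithmetic is sound. The 0.0456 error rate belongs to whatever section 2.3 counts, and to healing only if the two definitions coincide.

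**Step 2: what a gap could do (assumption, not in the documents).** Let H be the true healing rate and f the share of non-healed subjects with no recorded revision or re-tear. Suppose also that every healed subject scores as a success. The section 2.3 rate is then H + (1 − H)f. At H = 0.75:

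| f | Section 2.3 rate | Chance of a pass, P(X ≥ 85 of 103) |
|---|---|---|
| 0 | 0.750 | 4.6% |
| 0.10 | 0.775 | 13.4% |
| 0.20 | 0.800 | 30.9% |
| 0.30 | 0.825 | 56.0% |

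The documents give no value for f. If some healed subjects had a revision for another reason, the gap could run the other way.

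**Step 3: reference rate for the outcome actually scored (assumed range).** The pass rule stays at 85 of 103, and P(X ≥ 85 | 103, 0.80) = 0.309. This one figure has two readings:
- If similar devices were 90% free of revision or re-tear, the 75% bound is a 15-point margin, and a device 10 points worse (80%) passes 31% of the time.
- If they were 80% free, the bound is a 5-point margin, and a device equal to them passes only 31% of the time.

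**Step 4: the two margins.** If 0.09 applied to E0 = 0.85, the null is 0.76.
- Critical value 86 of 103, exact alpha 0.0438, power at 0.85 = 0.722.
- The first sample size with power of at least 0.80 is 126, above 109.

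**Step 5: a known failure who misses the visit.**
- Excluded: 85/103, p = 0.0456, one-sided 95% exact lower limit 75.2%. Pass.
- Counted: 85/104, p = 0.0670, lower limit 74.4%. No pass.

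**Step 6: 425 days.** If this is the event horizon, a visit at day 365 leaves 425 − 365 = 60 days unobserved.

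**The case against.** The best defence is that section 2.3 simply puts a vague synopsis into operation. Re-tear can be seen as one of the clinical outcomes the synopsis mentions, calling a re-tear is itself a judgement about the repair, and section 2.3 labels its rule the primary endpoint and uses the word success, which section 2.1 tests. The synopsis is marked as copied from the approved protocol, and neither the full protocol nor the case report form was supplied, so a link may exist there. What stands is that section 2.3 is relevant to healing. But a shared label is not a stated equivalence, and on this reading patient-reported outcomes still drop out of the scoring.

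On the side points the defence is stronger:

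- **Margin.** The 0.09 is attached to survivorship and may belong to a separate implant-survival analysis. At an assumed reference rate of 92% it would give about 80% power with 103 subjects. The 72% and the 126 apply only if it shares the 85% reference, and section 2.2 does not say.
- **Known failures.** A documented revision is neither undetermined nor unavailable, so the censoring rule need not touch it. However, the loss-to-follow-up sentence is separate, and the data it retains go to interim and survivorship calculations, not to the primary analysis. The planned sensitivity analyses do not settle the primary result. The 85/103 against 85/104 comparison sits exactly at the boundary. It shows that one subject can decide the result, not how likely that is.
- **425 days.** An upper visit limit is a plausible reading, and then there is no gap. This is only a request for clarification.

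**Conclusion.** The concern holds and should be fixed before analysis. The plan names and tests healing but scores freedom from revision or re-tear, and no supplied section connects them. A pass would show that the section 2.3 rate exceeds 75%. It would be indirect evidence on healing and would not establish a healing rate above 75% in the synopsis's sense.

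Neither the size nor the direction of the gap can be derived from the documents; the pass probabilities under f, and under reference rates of 80% and 90%, rest on assumed values. Two consequences are firm within their conditions: power of 72% instead of 80% if the 0.09 margin shares the 85% reference, and a result at the critical value that turns on one excluded known failure. The sample-size calculation itself is correct.

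**What to change.** 1. Keep the section 2.3 rule as the single primary endpoint and call it freedom from documented revision or re-tear in the synopsis, 2.1 and 2.2, replacing the healing and survivorship wording for the primary outcome.
2. State that E0 = 85% and the margin refer to that outcome and give their justification, or restate them and recompute power.
3. Use one margin, or state that 0.09 belongs to a separate implant-survival analysis and give its reference rate.
4. State in 2.2 and 2.3 that a documented revision or re-tear is a failure even if the one-year visit is missed. Only subjects with neither a documented event nor a one-year assessment are excluded, and these go to the sensitivity analyses.
5. State whether 425 days is the event horizon or the visit window.
6. Limit the primary conclusion to freedom from documented revision or re-tear, with patient-reported and clinical scores as secondary evidence on healing.

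The choice of definition is the sponsor's. If a healing conclusion is wanted, section 2.3 must score the investigator's healing assessment against a stated criterion, and E0, margin and power must be justified again for it.

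**Cost.** The main route needs changes of wording in four places and no new data collection. Because the synopsis is copied from the approved protocol, the protocol may need the same change. The conclusion becomes narrower, and a source is needed for E0 and the margin. If that source changes them, 103 subjects may not suffice. Counting known failures who miss the visit can only lower the observed success rate.

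### The primary success rule in SAP section 2.3 carries a qualifier that, read literally, scores a revision or re-tear already on the case report form as a success

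*Combined protocol and SAP*

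**What the plan says.** Section 2.3 (Data Analysis) is the only place where the primary endpoint becomes a scoring rule. It sets the time of assessment: "The primary endpoint will be determined at the only clinical assessment, about one year from the index surgery". It then defines success: "The absence of a revision surgery or re-tear not previously noted on the case report form will denote a success", with the window given as "within 425 days from index surgery". The remainder are dealt with in one sentence: "All other cases will be a failure and have a documented revision surgery or re-tear".

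Section 2.1 (Sample Size) describes the same rate in other terms: "The overall success rate will be calculated based on the percentage of subjects who have successful healing". It tests that rate against a benchmark, "E0 = 85%, the expected success rate of similar devices", less a margin of 0.10, so the null rate is 75%.

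The synopsis describes retrospective inclusion followed by one further contact: "Prospective follow-up visit at 1 year postoperative".

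**The concern.** The qualifier at the end of the success definition restricts which events count against the device. Suppose a subject was revised at month 5 and the revision was entered on the CRF from existing records. At the 1-year assessment this subject has no event that was previously un-noted, so the success definition is met. A second subject with the same revision, first written down at the 1-year visit, is a failure. On this reading the outcome turns on when the event was recorded and not on whether the repair failed.

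The affected quantity is the numerator of the only powered hypothesis test in the plan. The study has no control arm, so nothing offsets a one-sided scoring error. Moving recorded failures into the success count can only raise the rate, which favours the device.

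**Working it through.** **Reading the two sentences together**

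| Subject | Success sentence, read literally | Failure sentence |
|---|---|---|
| No event by day 425 | Success | Not reached |
| Event first recorded at the 1-year visit | Not a success | Failure |
| Event already on the CRF before the visit | Success | Not reached if it covers only the remainder; failure if it is taken to cover every documented event |

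The third row is the problem. If the failure sentence is a residual category, as its opening words indicate, the subject is a success. If it covers every documented event, the two sentences disagree about the same subject. Neither section 2.1, section 2.2 nor the synopsis settles which is meant.

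**Reproducing the stated design**

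Inputs from section 2.1: E0 = 0.85, margin 0.10, one-sided alpha 0.05, 103 evaluable subjects, 5% loss to follow-up.

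- Null rate: 0.85 − 0.10 = 0.75.
- Critical value: the smallest r with P(X ≥ r | n = 103, p = 0.75) ≤ 0.05 is r = 85.
- Attained alpha: P(X ≥ 85 | 103, 0.75) = 0.0456.
- Power: P(X ≥ 85 | 103, 0.85) = 0.803, in line with the stated 80%.
- Enrolment: 103 / 0.95 = 108.4, rounded up to 109, as stated.

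**Sensitivity at the threshold**

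Exact (Clopper-Pearson) one-sided 95% lower limits:

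- 85/103 (82.5%): 75.2%, pass.
- 84/103 (81.6%): 74.1%, fail.

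One subject moves the rate by 1/103 = 0.97 percentage points. At the threshold, that is enough to change the conclusion.

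**Hypothetical effect on the false-pass probability**

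Let p be the true event-free rate and f the share of failures recorded before the visit and scored as successes. The rate that the test sees is q = p + f(1 − p). Take p = 0.75, the null boundary. The documents do not give f, so the values below are assumptions.

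| f | q | P(X ≥ 85, n = 103, rate q) |
|---|---|---|
| 0 | 0.7500 | 4.6% |
| 5% | 0.7625 | 8.0% |
| 10% | 0.7750 | 13.4% |
| 20% | 0.8000 | 30.9% |

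At p = 0.75 the expected number of failures is 103 × 0.25 = 25.75. A share of 5% is therefore about 1.3 subjects and 20% about 5.2.

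**The case against.** The strongest reply is that the ordinary intent is visible in the surrounding text. The window runs from the index surgery and not from the visit. The failure sentence speaks of events that are documented, and a month-5 revision on the CRF is documented. Section 2.3 also limits the adverse event summary to the period before any revision or re-tear, so such events are expected to be known and dated. Section 2.2 plans a Kaplan-Meier analysis of implant survival and section 2.3 a full adverse event listing; both should make early revisions visible.

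The qualifier also has innocent explanations. It may be meant to set aside the tear present before surgery. It may be a garbled way of saying that no event has been noted on the form. It may attach to re-tear alone, although a re-tear noted earlier would then still score as a success.

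Much of this stands. A reader might infer that the sponsor will count early failures as successes; the documents do not support that, and the context points the other way. A reader might also infer that many failures will be on the CRF before the visit. Retrospective inclusion makes this plausible, but there is only one clinical assessment and no section describes an earlier CRF entry of revisions or re-tears. Nor are the two sentences in outright contradiction: they conflict only if the failure sentence is taken to reach beyond the remaining cases.

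What does not stand is the idea that context cures the rule. The Kaplan-Meier curve and the listing do not correct the binomial endpoint, and no section says what the qualifier refers to. With several readings open, the choice would fall to whoever programs the endpoint, possibly after the data are seen.

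**Conclusion.** The point holds as a defect in the wording of the primary endpoint and should be fixed before analysis. One natural reading of the success sentence classes an already recorded revision or re-tear as a success, and no other text overrides it. Confidence is high that the rule is ambiguous; it is not high that subjects will be mis-scored.

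On the literal reading the bias has one direction, upward, and a single subject is enough to move 84/103 to 85/103. The false-pass figures of 8.0%, 13.4% and 30.9% are illustrations. They require the literal reading to be applied, a true rate of exactly 75%, 103 evaluable subjects and an assumed share of failures recorded earlier. They should not be quoted as the error rate of this trial.

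**What to change.** Delete the qualifier about prior notation on the CRF and define the endpoint by event date, keeping the 425-day limit. Suggested text for section 2.3:

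> Success is the absence of any revision surgery or re-tear of the index repair occurring after the index surgery and within 425 days of it, whenever and wherever it was first recorded; any such event is a failure.

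If the phrase was meant to exclude tears present before the index surgery, the event-date rule already does so and no further wording is needed.

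The cost is one sentence in the SAP. No new data or visits are needed, and the sample size stays at 103 evaluable and 109 enrolled. The reported success rate may be lower than under the literal reading, by an amount that depends on how many events were recorded before the 1-year visit.
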